OFFICIAL TITLE:

*THE EFFECTS OF PROBIOTICS ON
METABOLIC BIOMARKERS,
INFLAMMATION, AND THE
ANTIOXIDANT SYSTEM IN PATIENTS
WITH TYPE 2 DIABETES MELLITUS*

Date: 17.04.2018

Background and Objectives

Type 2 diabetes mellitus (T2DM) prevalence has increased alarmingly due to obesity and sedentary lifestyle trends [1, 2]. T2DM causes end-stage renal failure, blindness, and lower limb amputations through progressive atherosclerosis, leading to 3-fold increased cardiovascular events and 2-fold increased cerebrovascular events [3, 4].

Recent data suggest that the gut microbiota plays a key role in development and progression of T2DM. This complex ecosystem of at least 10^{14} different bacteria affects energy homeostasis through the microorganism-gut-brain axis [5, 6]. Gut microbiota changes can alter enteroendocrine signals and gut hormones that regulate β -cell function, insulin secretion, and energy homeostasis [7]. The gut microbiota can affect the host's inflammation response and energy metabolism, in other words, alteration of the gut microbiota can affect glucose and lipid metabolism and insulin action. One of the most effective methods of maintaining the balance of the gut microbiota is the use of probiotics, defined as live microorganisms that, when given in adequate amounts, show host-specific benefit [8]. Recently, a growing number of studies have found that probiotics can alter gut flora, improve total cholesterol (Total-C) and Low-Density Lipoprotein Cholesterol (LDL-C) levels [9–11], and reduce blood glucose levels and insulin resistance [12, 13]. Nowadays, oxidative stress is also suggested to be a mechanism underlying diabetes and its complications. Antioxidant mechanisms of probiotics include scavenging of reactive oxygen species, metal ion chelation, enzyme inhibition, reduction activity, and inhibition of ascorbate autoxidation [14].

Modification of gut microflora with probiotics may be seen as a novel tool for the regulation of glucose metabolism and improvement of oxidative stress in T2DM. Increased severity of beta cell dysfunction was positively correlated with increased high-sensitivity C-Reactive Protein (hs-CRP) concentrations [15].

Although T2DM is recognized as a chronic inflammatory disease, the role of probiotics and prebiotics in its management remains insufficiently explored, and existing evidence regarding their overall efficacy in health and disease is inconsistent [16].

Regulation of gut microbiota through dietary interventions (e.g., probiotic intake) may be beneficial in reducing inflammation [hs-CRP and Ceruloplasmin (Cp)] and oxidative stress [Glutathione (GSH) and Malondialdehyde (MDA)], as well as regulating glucose and lipid metabolism in T2DM. The aim of this study was to investigate the effects of probiotics on glucose and lipid metabolism, inflammation and antioxidant system in patients with T2DM.

Methods

Trial design

This was a single center, prospective controlled study conducted at the Internal Medicine Outpatient Clinic of Ege University Faculty of Medicine between July 2020 and June 2023. The study included a screening visit, a baseline visit (D0) and one follow-up visit during a 60-days supplementation period. The primary outcomes of the study were defined as the effects of the intervention on inflammatory markers, specifically focusing on a significant decrease in hsCRP and Cp levels, and oxidative stress markers, including a significant reduction in MDA levels and a significant increase in reduced GSH levels. Secondary outcomes included assessing the metabolic and lipid profile changes, which specifically targeted a significant decrease in Fasting Blood Glucose (FBG), Postprandial Blood Glucose (PPBG), and Glycated Hemoglobin (HbA1c), alongside a reduction in LDL-C and Triglyceride (TG) levels, and an increase in High-Density Lipoprotein Cholesterol (HDL-C) levels.

Trial participants

Power analysis was performed and the sample size was calculated as 79 with a statistical power of 80% and an effect size of 0.35. Since two groups were to be studied, 80 patients were planned to participate in the study to equalize the number of participants.

This study included adults aged 35-65 years who were diagnosed with T2DM according to American Diabetes Association guidelines, who volunteered to participate in this study. Exclusion criteria were as follows: Use of any systemic antibiotics, multivitamins, minerals, herbal medicines, prebiotic, probiotic and postbiotic supplements in the last 3-6 months, any inflammatory bowel disease, severe renal dysfunction or hepatic dysfunction, immunodeficiency diseases, acute infection, rheumatoid arthritis, cancer history, history of alcohol abuse or drug dependence, pregnant or lactating women. Dietary habits, physical activity, and glucose-lowering therapy of the participants were not intervened during the study.

Participants were allocated sequentially according to order of presentation (alternate allocation). According to the order of presentation to the outpatient clinic, the first patient who met the inclusion criteria was included in the probiotic group and the second patient who presented to the outpatient clinic was included in the control group. Patients in the intervention group were given a probiotic supplement containing *Lactobacillus acidophilus*, *Lactobacillus rhamnosus*, *Bifidobacterium lactis* and *Lactobacillus paracasei*, each containing 1.25 billion live microorganisms, without vitamins and minerals, twice a day in addition to their current treatment for 12 weeks (Probiotic group). Patients in the control group were not given any

additional treatment and were allowed to continue their antidiabetic treatment for 12 weeks (Control group). Participants taking probiotics were instructed to discontinue probiotic intake if they experienced any serious adverse events requiring intervention. The probiotic product was supplied without placebo equivalent, and due to COVID-19-related supply limitations no identical-appearing placebo powder could be obtained. Sociodemographic data and medical data were recorded for all participants.

Anthropometric Measurements

Body weight, height, waist (WC) and hip circumferences (HC) were collected following the standardized procedures recommended in the World Health Organization Expert Committee Guidelines for physical examination at baseline and after 12 weeks [17]. Body mass index (BMI) (kg/m^2) and waist-to-hip ratio (WHR) (WC/HC) were calculated.

A Food Frequency Questionnaire (FFQ)

A Food Frequency Questionnaire was employed to determine how often specific food groups or individual food items were consumed. The frequency of consumption was recorded on a daily, weekly, biweekly, or monthly basis, providing insight into participants' overall dietary patterns. The FFQ is a commonly used tool to assess the relationship between dietary habits and health outcomes and can be adapted in various ways depending on the researcher's objectives. Food items can be listed individually or grouped according to categories such as full-fat, low-fat, or fat-free options [18]. The FFQ consisted of 68 individual food items clustered into five main food groups. In this study, the FFQ included five main food groups: dairy products, meat-egg-legumes, fruits and vegetables, cereals, fats and sweets, and beverages. Participants were asked to indicate how often they consumed each item (e.g., 1-2 times daily, 1-3 times weekly, 4-6 times weekly, once every two weeks, once monthly, or never), which enabled the calculation of their food consumption frequency over the past month.

The International Physical Activity Questionnaire (IPAQ)

When applying the IPAQ, participants were asked about their vigorous physical activity, moderate physical activity, and walking duration in the last seven days. Additionally, the number of days per week they performed these activities and time spent sitting were determined [19]. The Turkish validity and reliability study of the questionnaire was conducted by Öztürk [20]. Scoring was calculated as Metabolic Equivalent of Task (MET) scores from the sum of duration and frequency of moderate activity, vigorous activity, and walking [21]. Categories:

- Category I: Inactive individuals (<600 MET-min/week)

- Category II: Minimum active individuals (600-3000 MET-min/week)
- Category III: Very active individuals (>3000 MET-min/week)

Ferrans and Powers Quality of Life Index[©] Diabetes Version- III

The scale was developed by Ferrans and Powers to measure quality of life in diabetic patients, consisting of 34 satisfaction and 34 importance items. It includes 5 subscales: Total quality of life, Health and Functioning, Social and Economic, Psychological/Spiritual, and Family scores [22]. Higher scores indicate better quality of life. The Turkish validity study was conducted by Ozer [23].

Eating Attitudes Test (EAT-26)

The EAT-26 was developed for Garner et al.[24]. The test consists of 26 items, and the total score is between 0-53. A score of 20 and above is defined as “abnormal eating behavior” and a score less than 20 is defined as “normal eating behavior”. The Turkish validity and reliability study was conducted by Erguney-Okumus and Sertel-Berk [25].

Biochemical measurements

Fasting blood samples were collected from the participants at baseline and week 12, following overnight fasting and after 2 hours of satiety. FBG, PPBG, HbA1c, Total-C, LDL-C, HDL-C, TG and hs-CRP were measured using an autoanalyzer. Serum MDA levels were determined by the thiobarbituric acid method [26], GSH levels by enzymatic recycling method [27] and Cp levels by colorimetric method [27] using a microplate reader.

References

4. Choi SH, Chae A, Miller E, Messig M, Ntanios F, DeMaria AN, et al. Relationship Between Biomarkers of Oxidized Low-Density Lipoprotein, Statin Therapy, Quantitative Coronary

Angiography, and Atheroma Volume. *J Am Coll Cardiol.* 2008;52:24–32. <https://doi.org/10.1016/j.jacc.2008.02.066>.

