OFFICIAL TITLE:

*THE EFFECTS OF PROBIOTICS ON
METABOLIC BIOMARKERS,
INFLAMMATION, AND THE
ANTIOXIDANT SYSTEM IN PATIENTS
WITH TYPE 2 DIABETES MELLITUS*

Date: 17.04.2018

Statistical Analysis Plan (SAP)

Statistical analysis was performed using SPSS 25.0 statistical package program. Data from all patients who completed the study were included in the statistical analysis. For descriptive findings, categorical variables were presented as numbers and percentages, and continuous variables were presented as mean, standard deviation, minimum value and maximum value. Kolmogorov-Smirnov normality tests were used to determine whether the data showed normal distribution. Pearson chi-square test was used to analyse categorical variables. Parametric tests (t test in independent groups, t test in dependent groups) were used in the analysis of normally distributed data, and non-parametric tests (Mann-Whitney U test, Wilcoxon Signed Rank Test) were used in the analysis of non-normally distributed data. Statistical significance level was accepted as $p<0.05$.

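### Arms are filled by predictable alternation, yet the SAP names no between-arm contrast, uses no baseline covariate and lists within-arm tests; add ANCOVA with the change comparison beside it

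*Protocol*

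**What the plan says.** **Allocation.** Protocol, Trial participants: "Participants were allocated sequentially according to order of presentation (alternate allocation". The rule is spelled out: "the first patient who met the inclusion criteria was included in the probiotic group and the second patient who presented to the outpatient clinic" went to control. No concealment step is described. Controls received nothing in addition to their usual treatment, and "no identical-appearing placebo powder could be obtained". The protocol does not claim randomisation. Trial design says "This was a single center, prospective controlled study".

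**Outcomes and sampling.** Trial design makes hs-CRP, ceruloplasmin (Cp), MDA and GSH primary, "specifically focusing on a significant decrease in hsCRP and Cp levels", with similar wording for MDA (fall) and GSH (rise). It does not say whether significance is judged between arms or within the probiotic arm. Biochemical measurements: "Fasting blood samples were collected from the participants at baseline and week 12".

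**Analysis.** The SAP is one paragraph. For continuous data it says "Parametric tests (t test in independent groups, t test in dependent groups) were used in the analysis of normally distributed data". Where normality fails, it substitutes the rank-based counterparts: Mann-Whitney between arms and Wilcoxon within arms. No model or covariate is named. The SAP does not say which variable enters the between-arm test, or which test decides a primary outcome.

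**The concern.** Three gaps meet here.

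- **The contrast is not named.** A comparison of week-12 values and a comparison of changes can lean in opposite directions on the same data when baselines differ. If the choice is not written down, it can be made after the results are seen.
- **The baseline value is not used as a covariate.** It is measured for every primary marker and would usually narrow the interval. In a non-random comparison it would also remove some kinds of imbalance, though not all.
- **Within-arm tests stand beside between-arm tests with no ranking.** A significant fall in the probiotic arm and none in the control arm is not evidence of a difference between arms, yet the outcome wording could be read as satisfied by it.

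Predictable allocation sharpens the first two points. When the next arm is known, baseline differences can arise by selection as well as by chance.

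**Working it through.** **Inputs.** 40 per arm (Protocol, Trial participants: 80 patients, two groups, read as equal arms). Two-sided 5% level (the SAP gives 0.05; two-sided is assumed). Baseline and follow-up values each have SD 1. The correlation r between them is not in the documents; I assume 0.5 and show 0.3 to 0.7. No treatment effect, normal data. The plan gives no figure of its own on this point to reproduce.

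**1. Size of a chance baseline difference d (probiotic minus control).** SE = sqrt(2/40) = 0.224 SD. P(|d| > 0.2) = 2 × [1 − Φ(0.2/0.224)] = 37%. P(|d| > 0.3) = 2 × [1 − Φ(0.3/0.224)] = 18%.

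**2. What each analysis does with a baseline difference.** This depends on how the difference arose.

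- *By chance, or by selection on the marker itself:* a fraction r persists to follow-up. The week-12 comparison moves by r·d, the change comparison by r·d − d = −(1 − r)·d, and ANCOVA by r·d − r·d = 0.
- *By a stable difference g between the arms, present equally at both times:* the week-12 comparison moves by g, the change comparison by g − g = 0, and ANCOVA by g − r·g = (1 − r)·g.

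For a difference of 0.3 SD:

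| r | Chance or marker selection: week-12 / change / ANCOVA | Stable gap: week-12 / change / ANCOVA |
|---|---|---|
| 0.3 | +0.09 / −0.21 / 0 | +0.30 / 0 / +0.21 |
| 0.5 | +0.15 / −0.15 / 0 | +0.30 / 0 / +0.15 |
| 0.7 | +0.21 / −0.09 / 0 | +0.30 / 0 / +0.09 |

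In the stable-gap case, simulation gives ANCOVA false-positive rates of about 16%, 12% and 8% at r = 0.3, 0.5 and 0.7; the change test stays at 5%. In the pure chance case all three analyses keep 5% over repeated trials, and only the single trial's estimate moves.

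**3. Hypothetical selection, r = 0.5.** Suppose half of the above-median patients were passed over in probiotic slots.

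- *Selection on the baseline marker:* week-12 −0.13 SD (9.0% false positives), change +0.13 SD (9.1%), ANCOVA 0.00 (5%).
- *Selection on another trait correlated 0.5 with both values:* week-12 −0.13 SD (9.1%), ANCOVA −0.07 SD (6.4%), change about 0 (5%).

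**4. Precision with no systematic imbalance.** The 95% half-width for week-12 values is t(78) × 0.224 = 0.445 SD. For change it is 0.445 × sqrt(2(1 − r)). ANCOVA values are from simulation, close to 0.445 × sqrt(1 − r²).

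| r | Week-12 | Change | ANCOVA | Narrower than week-12 | Narrower than change |
|---|---|---|---|---|---|
| 0.3 | 0.445 | 0.527 | 0.426 | 4% | 19% |
| 0.5 | 0.445 | 0.445 | 0.387 | 13% | 13% |
| 0.7 | 0.445 | 0.345 | 0.319 | 28% | 8% |

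**5. Within-arm tests.** Let both arms fall by the same amount f. The SD of change is sqrt(2(1 − r)). The paired t test with n = 40 has noncentrality f·sqrt(40)/sqrt(2(1 − r)) and gives a significant fall with probability p. The misleading pattern, significant with probiotic and not in control, has probability p(1 − p).

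| r | f = 0.2: p, p(1 − p) | f = 0.3: p, p(1 − p) |
|---|---|---|
| 0.3 | 0.180, 15% | 0.346, 23% |
| 0.5 | 0.234, 18% | 0.457, 25% |
| 0.7 | 0.357, 23% | 0.666, 22% |

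**The case against.** The strongest reply concerns the choice of model. ANCOVA is exact only if the baseline difference came from chance or from selection on the marker. No document says marker values were known when patients were allocated. If anyone did anticipate the next arm, a visible trait would be a more natural basis, and then the change comparison can be the unbiased one. That stands. ANCOVA cannot be offered as a cure for alternation, and the change comparison must be shown with it.

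It is also fair that chance imbalance arises equally under randomisation, and that the SAP includes between-arm tests. The within-arm hazard applies only if those tests are allowed to decide, which no section says. But no section rules it out either. The unnamed contrast, the unused covariate and the unranked tests are all gaps whether or not anyone steered patients.

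A reader might infer that patients were steered, or that the trial passes itself off as randomised. Neither is supported. No steering is documented, the order of consent and assignment cannot be judged from the available text, and the protocol openly calls the allocation alternate.

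**Conclusion.** The point holds as a should-fix matter of analysis. Without any steering, the plan leaves open two between-arm readings that a chance baseline difference of 0.3 SD would push 0.3 SD apart at any r (r·d plus (1 − r)·d equals d). It forgoes an interval 4 to 28% narrower than the week-12 reading, or 8 to 19% narrower than the change reading, over r = 0.3 to 0.7. It also leaves room for a within-arm pattern that arises in about 15 to 25% of trials when both arms fall equally by 0.2 to 0.3 SD.

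The figures rest on 40 per arm, normal data, equal SDs and an assumed r. It would go too far to say that baseline adjustment makes the alternate allocation safe: a stable 0.3 SD gap leaves ANCOVA off by 0.21, 0.15 or 0.09 SD at r = 0.3, 0.5 or 0.7. Selection on unmeasured factors remains whichever analysis is chosen.

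**What to change.** 1. Add to the SAP, for hs-CRP, Cp, MDA and GSH: a between-arm ANCOVA of the follow-up value on arm and the baseline value of the same marker, reported as an adjusted difference with 95% CI. Use a log scale, with a ratio of geometric means, for any marker whose residuals are clearly skewed; hs-CRP is the likely one.
2. Report the unadjusted between-arm comparison of change, on the same scale, beside it as the check against stable arm differences. If the two disagree, call that marker inconclusive. Define disagreement in the SAP, for example opposite directions or only one interval excluding no difference.
3. State that within-arm tests are descriptive and that no primary conclusion rests on them.
4. Date and disclose the change. Trial design reports conduct from July 2020 to June 2023 in the past tense, so say whether results had been seen. If they had, label the ANCOVA post hoc, state which between-arm contrast had been used, and show both.
5. Describe the comparison as non-random (alternate) allocation wherever arms are compared, and limit causal wording.

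Trial design gives a 60-day supplementation period, while Trial participants and Biochemical measurements give 12 weeks. These must be reconciled before the follow-up time in the model is fixed.

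**Cost.** Four linear models and four change comparisons on values already collected, plus wording; no new visits or samples. The price is a disclosed late change, a somewhat weaker claim (two analyses must agree, and the change comparison is the less precise one), and a ratio scale for any logged marker. The allocation itself can no longer be repaired.

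### Strict alternation makes the next arm predictable while eligibility and consent are judged, and the entry wording for the control slot needs reconciling with the study's single set of criteria

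*Protocol*

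**What the plan says.** The allocation rule is in the protocol, Methods, Trial participants. Assignment alternates by order of presentation to the clinic: "the first patient who met the inclusion criteria was included in the probiotic group and the second patient who presented to the outpatient clinic" went to the control group. Controls received no additional treatment, and the protocol explains that no matching placebo could be obtained.

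Earlier in the same section, entry is described once for the whole study: "This study included adults aged 35-65 years who were diagnosed with T2DM according to American Diabetes Association guidelines, who volunteered to participate in this study". The exclusions that follow are not split by arm. Under Trial design: "The study included a screening visit, a baseline visit (D0) and one follow-up visit". Neither document says at which visit the arm was assigned, who judged eligibility, or whether consent came before or after the arm could be known. Neither describes a random sequence or any concealment.

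**The concern.** Alternation has no random element. Once one patient has been allocated, the arm of the next is settled. Anyone deciding whether the next patient qualifies can act on that knowledge, deliberately or not, and a patient can be told what joining would mean before deciding.

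There is room for discretion here. The renal and hepatic exclusions turn on whether dysfunction is severe. The look-back for antibiotics and supplements is given as a range of three to six months, not one fixed window. Entry also depends on volunteering, and with no placebo the offer is visibly different in the two arms.

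Several exclusions, such as acute infection, rheumatoid arthritis, inflammatory bowel disease and recent antibiotic or probiotic use, could plausibly shift the primary markers (hs-CRP, ceruloplasmin, MDA, GSH). Stricter or looser entry in one arm could therefore feed directly into the primary comparison. The SAP's tests are unadjusted and use completers only, so the analysis does not counter this. Baseline adjustment would correct only what was measured.

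**Working it through.** The plan states no figure on this point, so there is none to reproduce. The check has two parts.

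**1. Is the next arm predictable?** The rule can be read in two ways.

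- Every patient who presents uses up a slot. The arm is then fixed on arrival, before any criterion is checked.
- Only eligible patients use up a slot. The arm of the next eligible patient is then the opposite of the last one allocated, and is known before that patient is screened.

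Under both readings the next arm can be predicted with certainty, against a 50% guess under simple concealed randomisation. This part does not depend on how the entry sentence is read.

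**2. What could selection do to the primary tests?** The inputs are:

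- 80 planned patients in two equal groups, so 80/2 = 40 per arm (protocol, Trial participants).
- Significance level 0.05 (SAP). The SAP does not give sidedness; two-sided is assumed.
- Imbalance b, in SD units, caused by selection. This is an assumption; the documents give no value.

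The imbalance can be thought of as (share of one arm that would not have been taken into the other) × (how far those patients differ). A 10% share differing by 0.5 to 1 SD gives 0.10 × 0.5 = 0.05 SD to 0.10 × 1 = 0.10 SD. Shares of 20% and 30% differing by 1 SD give 0.2 and 0.3 SD.

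The standard error of a difference in means, in SD units, is √(2/40) = 0.2236. With no true effect, the test statistic is shifted by δ = b/0.2236. By normal approximation, the false-positive rate is 1 − Φ(1.96 − δ) + Φ(−1.96 − δ).

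| Assumed b (SD) | δ | False-positive rate |
|---|---|---|
| 0 | 0 | 5.0% |
| 0.05 | 0.224 | 5.6% |
| 0.10 | 0.447 | 7.3% |
| 0.20 | 0.894 | 14.5% |
| 0.30 | 1.342 | 26.9% |

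These rates are for one marker in one between-arm test. I have not expressed b as a share of the planned effect size of 0.35, because the protocol does not say what kind of effect size that is.

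**The case against.** The entry sentence can be read elliptically: the first eligible patient to probiotic, the second to control. The protocol supports that reading. Its criteria cover the whole study, the screening visit is not limited to one arm, and the allocation text speaks of participants. A reader might infer that controls were admitted without an eligibility check, so that screened volunteers were compared with whoever came next. The documents do not support this: nothing says that controls skipped screening or that any ineligible control was entered.

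A reader might also infer that eligibility was judged after the arm had been assigned. The order of screening and assignment is not stated, so the arm can be called predictable at that moment, but not known or already assigned.

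The size is assumed, and at the lower end it is small: 0.05 to 0.10 SD takes a 5% error rate only to about 5.6% to 7.3%. Finally, neither document claims randomisation, and the text reports conduct from July 2020 to June 2023, so advice on concealed assignment comes too late for patients already entered.

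All of this stands. It does not remove the predictability, which follows from alternation under either reading, or the silence on when eligibility and consent were fixed.

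**Conclusion.** The concern holds in this form: alternation by order of presentation, with no concealment described and no placebo, leaves the next arm predictable while eligibility and willingness to take part are being settled, so selection by arm is possible. Separately, the entry wording differs between the two slots and must be reconciled with the single set of criteria; on its own it may be no more than drafting.

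The documents show neither that selection took place nor how large it would be. The range of about 6% to 27% for the false-positive rate rests on an assumed imbalance of 0.05 to 0.3 SD, 40 patients per arm, a two-sided 5% test and a normal approximation. It is enough to require cautious causal wording and a check of the records. It is not enough to say that the arms came from different populations or that the result is invalid.

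**What to change.** **Wording.** State that every patient, in either arm, must meet all inclusion criteria and no exclusion criterion, and must consent, before an arm is assigned. Say who judges eligibility.

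**Any patient not yet enrolled.** Enter the patient in a numbered log once eligibility and consent are fixed, then open the next assignment from a concealed random list in blocks of varying size.

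**Patients already enrolled.**

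- Re-check both arms against the full criteria, blind to outcome and, if possible, to arm. Checking controls alone would itself apply eligibility differently by arm.
- Report by arm the numbers presented, screened, ineligible and declined, where records allow.
- Repeat the primary comparison in the patients of both arms who verifiably met all criteria.
- State explicitly that the trial is non-randomised, and limit statements about effects of the intervention accordingly.

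**Cost.** A few sentences, a screening log and a record check. For any new enrolment, the arms may end slightly unequal; varying blocks keep that small.
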